4.5 Subgroup Analyses and Effect of Baseline Factors

Descriptive summary statistics for the primary efficacy endpoint will be presented for the subgroup of habitual BIOTRUE formulation users. [REDACTED]

[REDACTED]

[REDACTED]

[REDACTED]

[REDACTED]

4.6 Interim Analysis for Efficacy

No interim analysis is planned for the study.

5 Safety Analysis Strategy

5.1 Safety Endpoints

The safety endpoints are:

- Adverse events
- Biomicroscopy Findings
 - Limbal hyperemia
 - Bulbar hyperemia
 - Corneal infiltrates
 - Other Findings
 - Conjunctival staining
 - Lid Papillae

- Corneal staining
- Device deficiencies

5.2 Safety Hypotheses

There are no formal safety hypotheses in this study. The focus of the safety analysis will be a comprehensive descriptive assessment of safety endpoints listed in Section 5.1.

5.3 Statistical Methods for Safety Analyses

The analysis set for all safety analyses is the safety analysis set as defined in Section 2.1. The safety variables will be summarized descriptively.

5.3.1 Adverse Events

The applicable definition of an Adverse Event (AE) is in the study protocol. All AEs occurring from when a subject signs informed consent to when a subject exits the study will be accounted for in the reporting.

Analysis and presentation of pre-treatment AEs will be separated from treatment-emergent AEs occurring during the study period. A pre-treatment AE is an event that occurs after signing informed consent but prior to exposure to the study lens care for period 1 and period 2. The period for treatment-emergent AE analysis starts from exposure to the study lens care for period 1 and period 2 until the subject completes or is discontinued from the study.

Descriptive summaries (counts and percentages) for ocular and non-ocular AEs will be presented by Medical Dictionary for Regulatory Activities (MedDRA) Preferred Terms. In addition to an overall presentation of AEs, reports will be generated for special classes of AEs such as treatment-related AEs and serious AEs. AEs leading to study discontinuation will be identified. Presentation of ocular AEs will be by eye.

Individual subject's listings will be provided for both pre-treatment and treatment-emergent AEs.

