CLDEQ-8 (Day 30)	CCP vs HMPS Superiority	Mixed effect repeated measure model. Baseline score as a covariate.

Sponsor: Alcon Research, Ltd.
[name]

Protocol Number: LCS739-P001

Safety:

Each safety variable will be summarized descriptively. AEs will be classified as treatment-emergent, based on treatment-specific exposure, or pre-treatment. Count and percentage will be provided by relationship to device, and separate tables will be generated for ocular and nonocular AEs. Counts and percentages in each grade category will be presented for each biomicroscopy parameter. Device deficiencies will also be tabulated. Supporting subject listings describing details of each safety variable will be provided. Listings describing details of AEs reported prior to usage of the study solutions will be presented separately from the safety analysis for the treatment-emergent AEs.

Sample Size Justification:

Sample size calculations for the primary endpoint are summarized below (one-sided $\alpha=0.05$).

Endpoint	Assumptions	Power	N
Primary			
CLDEQ-8	SD=10 (paired differences)	80% Detectable difference=3	36 per each of the 2 crossover sequences

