8 SUBJECT POPULATION

Approximately 120 subjects (approximately 8 to 20 subjects per site) are to be randomized at approximately 9 United States (US) sites to achieve approximately 110 subjects completed. An advertisement may be used to aid recruitment. The advertisement will be submitted to the IEC/IRB for approval. The IRB approved Pre-screening questionnaire will be provided before taking the consent.

The enrollment for the study is planned for 6 weeks. The expected duration of subject participation in the study (3 scheduled visits) is 30 ± 3 days per study period (up to 66 days total). The complete inclusion and exclusion criteria are presented in Section [8.1](#) and Section [8.2](#).

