9 TREATMENTS ADMINISTERED

Upon completing Pre-screening Questionnaire and satisfying the relevant pre-screening criteria, subjects will sign informed consent and then be considered enrolled into the study. A subject ID number will be assigned to enrolled subjects by entering the subject into the electronic data capture (EDC) system. Subjects eligible after Screening at Visit 1 will be randomized (1:1) to receive either CCP or HMPS to care for their lenses in Period 1 of the study. For Period 2, the contact lens solution that was not allocated for use in Period 1 will be dispensed. The randomization will be stratified by HMPS (BIOTRUE vs. Other MPS). Throughout the study, designated unmasked site personnel at the investigational site will be responsible for the accounting of all study products and will ensure that the study products are not used in any unauthorized manner.

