11	Unmasked coordinator to assign/dispense the study lens care solution for Period 1 per randomization scheme. 
1) HMPS purchased by the subject or provided by the site –or-2) Investigational Masked CCP Kit with Kit # and B&L Sensitive Eyes Saline. Educate on instructions for use and emphasize for the first-time hydrogen peroxide CLC users the warnings and use of the correct lens case with the product.
12	Assess and record any adverse events (AEs) that are reported or observed from the time of informed consent (see Section 12).
13	Record any device deficiencies that are observed or reported.
14	Schedule Visit 2 (Period 1 Follow-up) to take place on Day 30 ± 3 days (scheduled 29 (± 3) days after Visit 1. Provide subject with Visit 2 reminder instructions: 
• The subject should bring the used lens case for the study period, along with their dispensed study solution used during the study period.

10.2.2 VISIT 2 – PERIOD 1/Day 30 & PERIOD 2/DAY 1

1	Document wear time compliance (days, hours) and lens care compliance. Collect used study lens care product(s) from the subject.
2	Obtain information on any changes in medical health and/or the use of concomitant medications since Visit 1.
3	Have subject complete the Subjective Questionnaire based on lenses worn and study solution used during the 30 day study period (CLDEQ-8, [REDACTED] [REDACTED] [REDACTED])
4	Conduct Snellen VA with worn lenses. For details refer to MOP.
5	[REDACTED]

6	Remove lenses and perform biomicroscopy assessments using slit-lamp examination scales. For details and order of staining procedures, refer to MOP. Perform subjective (manifest) refraction assessment and BCVA assessment (as needed). For details refer to MOP.
7	Assess and record AEs that are observed or reported (See Section 12).
8	Record any device deficiencies that are observed or reported.
9	Dispense a new pair of habitual lenses and perform Snellen VA with new lenses being dispensed at the visit. For details refer to MOP. For two-week replacement lens wearers, provide the subject an extra pair of study lenses for replacement at two weeks. Contact the subject at approximately 15±1 days of the study period to remind the subject to replace their lenses and document date of replacement in the source.

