11.2 Analysis Data Sets

11.2.1 Safety Analysis Set

Safety analyses will be conducted using the safety analysis set on a treatment-emergent basis. The safety analysis set will include all subjects/eyes exposed to the newly dispensed habitual lenses for the study disinfected with at least one study lens product evaluated in this study. For treatment-emergent safety analyses, subjects/eyes will be categorized under the actual lens care product exposed.

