1.3 Randomization

A member of the Randomization Programming group at Alcon who is not part of the study team will generate the randomized allocation schedule(s) for study contact lens solution assignment. Subjects eligible after screening at Visit 1 will be randomized (1:1) to receive either CCP or HMPS to care for their lenses in Period 1 of the study. For Period 2, the contact lens solution that was not allocated for use in Period 1 will be dispensed. The randomization will be stratified by HMPS (BIOTRUE vs. Other MPS). Randomization will be blocked to ensure a balance of study treatment (lens care sequence) allocation within investigational sites and strata. Randomization will be implemented in an Electronic Data Capture (EDC) system.

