2.1 Safety Analysis Set

The safety analysis set will include all subjects/eyes exposed to the newly dispensed habitual lenses for the study disinfected with at least one study lens product evaluated in this study. Safety analysis will be conducted using the safety analysis set on a treatment-emergent basis. For treatment-emergent safety analysis, subjects/eyes will be categorized under the actual lens care products exposed.

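### Does the treatment-emergent AE window in SAP 5.3.1 count Period 2 events under both products and so dilute the CCP-HMPS safety comparison?

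*SAP*

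**What the plan says.** SAP 5.3.1 divides AEs into pre-treatment and treatment-emergent. The treatment-emergent period "starts from exposure to the study lens care for period 1 and period 2 until the subject completes or is discontinued from the study". That one sentence covers both periods, and its only stated end is study exit. It names neither solution.

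Which product an event belongs to is dealt with in three other places:

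- Protocol synopsis, Safety: "AEs will be classified as treatment-emergent, based on treatment-specific exposure, or pre-treatment".
- Protocol 11.2.1: "subjects/eyes will be categorized under the actual lens care product exposed".
- SAP 2.1: "For treatment-emergent safety analysis, subjects/eyes will be categorized under the actual lens care products exposed".

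The design uses one solution per period. Under Protocol section 9, eligible subjects "will be randomized (1:1) to receive either CCP or HMPS to care for their lenses in Period 1". SAP 1.3 adds: "For Period 2, the contact lens solution that was not allocated for use in Period 1 will be dispensed". Protocol 9.2 gives each period its own length of 30 ± 3 days. At Visit 2 (Protocol 10.2.2), step 1 includes the instruction "Collect used study lens care product(s) from the subject", and step 10 dispenses the Period 2 solution.

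Safety is descriptive throughout. Protocol 11.7 rules out inferential testing, and SAP 5.2 states that there are no formal safety hypotheses.

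**The concern.** In a crossover without washout, the first product's AE window normally closes when the second product is started. SAP 5.3.1 does not write that closure down. Taken alone, it places a Period 2 event in a CCP-first subject after first CCP exposure and before study exit, so inside a CCP window, and also inside the HMPS window. The attribution rules classify subjects or eyes rather than events, and by Period 2 a subject has been exposed to both solutions.

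The by-product AE counts are a main part of the safety evidence, with no test behind them. If Period 2 events went under both products, each product would absorb events that arose on the other, and a real excess on CCP would move toward no difference. Protocol 5.2 names chemical burn from unneutralised peroxide as a risk for wearers new to peroxide systems, so blurring the comparison would matter.

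The pre-treatment definition in the same section can raise a similar worry, because it refers to exposure in Period 1 and Period 2 together, and a Period 1 event does come before Period 2 exposure.

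**Working it through.** **Inputs.** About 120 subjects are randomized 1:1, so about 60 per sequence. Protocol section 8 plans this "to achieve approximately 110 subjects completed". The documents give no AE rate and no expected safety difference, so there is no figure of the plan's own to reproduce. Let c and h be the per-period AE risks on CCP and HMPS. Values given to them below are assumptions.

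**1. Attribution to the product in use.** Each product is used by 60 subjects in Period 1 and 60 in Period 2.

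- CCP events = 120c; HMPS events = 120h
- Difference = 120(c − h)

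**2. Every Period 2 event also counted under the Period 1 product.**

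- CCP = 120c + 60h
- HMPS = 120h + 60c
- Difference = 60(c − h), a factor of 60/120 = 0.50 whatever c and h are

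Example with assumed c = 10% and h = 5%:

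| Rule | CCP events | HMPS events | Difference |
|---|---|---|---|
| Product in use | 12 | 6 | 6 |
| Double counted | 12 + 3 = 15 | 6 + 6 = 12 | 3 |

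By subject incidence, double counting gives:

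- CCP: c + h(1 − c)/2 = 0.10 + 0.05 × 0.90/2 = 12.25%
- HMPS: h + c(1 − h)/2 = 0.05 + 0.10 × 0.95/2 = 9.75%

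The difference is 2.5 points instead of 5.0, and the ratio is 1.26 instead of 2.00.

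**3. How far the factor moves under double counting.**

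- Dropout: if a fraction f enters Period 2, the product-in-use difference is 60(1 + f)(c − h) and the double-counted difference stays at 60(c − h). The factor is 1/(1 + f). With f = 110/120 = 0.917 it is 0.522.
- Period effect: if Period 2 risks are k times those of Period 1, the factor is 1/(1 + k). That is 0.33 at k = 2 and 0.67 at k = 0.5.
- Unequal sequences, at c = 10% and h = 5%: the chance of an event in either period is 1 − 0.90 × 0.95 = 0.145.
  - With 56 CCP-first and 64 HMPS-first, CCP = (56 × 0.145 + 64 × 0.10)/120 = 12.10% and HMPS = (64 × 0.145 + 56 × 0.05)/120 = 10.07%. The factor is 2.03/5 = 0.41.
  - With 64 and 56, CCP = 12.40% and HMPS = 9.43%. The factor is 2.97/5 = 0.59.

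The arithmetic of halving is therefore sound, provided that events are double counted.

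**4. Do the documents call for double counting?**

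- *What the SAP 5.3.1 sentence does.* It follows the statement that pre-treatment AEs are presented apart from treatment-emergent ones, and it sets the boundary between the two. For that purpose, study exit is the correct end: an event in either period is treatment-emergent.
- *What decides the product.* The synopsis ties the classification to exposure specific to a treatment. A window that assigned every later event to the Period 1 product would not be specific to a treatment. Protocol 11.2.1 speaks of the product, in the singular, actually used.
- *When Period 1 exposure ends.* Used product is collected at Visit 2 and the other solution is dispensed at the same visit. That gives the exposure rule a definite switch point.
- *The pre-treatment definition.* It requires the event to precede exposure in both periods. A Period 1 event does not precede Period 1 exposure, so it fails. Protocol 11.7 confirms this by referring to events before exposure to the study solutions.

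Nothing in either document says that a Period 2 event is also counted under the Period 1 product. With the exposure rule applied, the factor is 1.00.

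**The case for a change.** The strongest counter-argument is that the three attribution passages show an intention without giving an operating rule. They sort subjects and eyes, SAP 2.1 uses the plural for products, and none assigns an event by its onset date. There is no washout, so every continuing subject changes solution at Visit 2. Two programmers could in principle build different AE tables and both cite the SAP. Treatment-emergent device deficiencies (SAP 5.3.3) are likewise listed without a stated window.

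Part of this stands. The onset-date rule is indeed unwritten, for AEs and for device deficiencies. What does not stand is that the two readings are equally supported. Double counting requires ignoring the synopsis wording on treatment-specific exposure and treating a solution already handed back as a current exposure. Assigning each event once, to the solution in use at onset, is the ordinary way to carry out the stated rule in a two-period crossover. SAP 5.3.1 also plans individual subject listings of both pre-treatment and treatment-emergent events, so the tables can be checked against individual events.

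**Conclusion.** The concern does not hold as a fault in the plan. SAP 5.3.1 leaves a detail unwritten, and the exposure-based attribution in the Protocol synopsis, Protocol 11.2.1 and SAP 2.1 supplies what an analyst needs to fill it. Followed together, the documents do not dilute the by-product AE counts.

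The halving describes a misreading. It is 0.50 only with full double counting, equal sequences, no dropout and no period effect. It is 0.52 with 110 of 120 entering Period 2, and lies between 0.33 and 0.67 over the other departures examined. If c = h there is no difference to dilute. All AE rates used are assumptions.

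Safety is reported as descriptive counts and percentages, with no test or hypothesis to be biased. The conclusion assumes that analysts apply the stated exposure rule and that AE onset can be placed before or after the Visit 2 switch. The documents do not list the AE form's fields, but separating pre-treatment from treatment-emergent events already requires onset timing. No change to the plan follows.

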5.3.2 Biomicroscopy Findings

Baseline is defined to be Visit 1. Each biomicroscopy parameter will be tabulated by its grade, at Baseline and Day 30. A shift table showing grade at baseline relative to Day 30 will also be presented for each parameter. For each biomicroscopy parameter, counts and percentages of eyes that experience an increase of ≥ 2 grades from baseline to any subsequent visit will be presented. A supportive listing will be generated which will include all biomicroscopy data from the affected visit for these eyes experiencing the increase of ≥ 2 grades, with the following variables: lens care solution, Investigator, subject, age, sex, visit, eye, parameter, baseline value, and value at the visit.

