8.2 Exclusion Criteria

1. Extended wear (sleeps in lenses one or more nights per week).

2. Any anterior segment infection, inflammation, disease, or abnormality that contraindicates contact lens wear as determined by the Investigator.
3. Any use of systemic medications or ocular medications for which contact lens wear could be contraindicated, as determined by the Investigator, including use of any topical ocular medications that would require instillation during contact lens wear.
4. Monocular subjects (only 1 eye with functional vision) or subjects fit with only 1 lens.
5. A known sensitivity to any ingredients in CCP.
6. Biomicroscopy findings observed during the Visit 1 slit-lamp examination that are moderate (grade 3) or worse in either eye.
7. Prior refractive surgery (eg, LASIK and PRK).
8. History of herpetic keratitis, ocular surgery, or irregular cornea.
9. A pathological dry eye that precludes contact lens wear.
10. Use of mechanical eyelid therapy or eyelid scrubs within 14 days before Visit 1 and not willing to discontinue during the study.
11. Enrollment of the Investigator or his/her staff, family members of the Investigator, family members of the Investigator's staff, or individuals living in the households of these individuals.
12. Enrollment of more than 1 member of the same household in the study.
13. Participation in any clinical study within 30 days of Visit 1.
14. Subjects who are currently using or have not discontinued RESTASIS, XIIDRA or a topical steroid within the past 7 days.

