10.3 Unscheduled Visits

Any visit that occurs between the regularly scheduled visits must be documented in the unscheduled visit pages of the eCRF. During all unscheduled visits, the following procedures should be conducted:

- Document wear time compliance (days, hours) and lens care compliance.
- Obtain information on any changes in medical health and/or the use of concomitant medications.
- Perform Snellen VA with lenses (as needed).
- Perform subjective (manifest) refraction (as needed).
- Perform BCVA assessment (as needed).
- Perform biomicroscopy.
- Record any AEs or device deficiencies that are observed or reported.
- Replace lenses and dispense additional study lens care solution for the study period if needed (as needed). Record all unplanned lens replacement dates in the source.
- Exit the subject from the study (if subject is discontinuing at the unscheduled visit).

If the subject is discontinuing at the unscheduled visit, the Early Exit visit eCRF should be completed rather than the eCRF form for an Unscheduled visit.

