10.4 Discontinued Subjects and Screen Failures

Discontinued subjects are those who withdraw or are withdrawn from the study after being randomized. Subjects may discontinue from the study at any time for any reason. Subjects

may also be discontinued from the study at any time if, in the opinion of the Investigator, their continued participation poses a risk to their health. Discontinued subjects will not be replaced (ie, their subject numbers will not be re-assigned/re-used).

If a subject is identified not to fulfill the eligibility criteria for study inclusion during the Screening visit (Visit 1), the subject will be screen failed and will not participate any further in the study. The EDC system will be updated to confirm the subject is a screen failure. The Investigator will explain to the subject the reason(s) why eligibility was not met and provide appropriate information/treatment, if required. The Exit form will be completed for all discontinued subjects and screen failures.

Should a subject exhibit any clinically relevant signs, symptoms, or other clinical observations that possibly could be associated with suspected sensitivity or intolerance to one of the study treatments, the Investigator must document those observations on an AE Form. Observations must also be reported for occurrences not associated with any study treatment (see Section 12.3, Procedures for Recording and Reporting AEs and SAEs).

Any subject who exits early from the study should undergo all procedures outlined at Visit 3/Exit. Additionally, the Exit Form must be completed and the reason for discontinuation must be identified and captured in EDC.

Finally, to ensure the safety of all subjects who discontinue early, Investigators should assess each subject and, if necessary, advise them of any therapies and/or medical procedures that might be needed to maintain their health.

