11.7 Safety Analysis

The safety endpoints for this study are AEs, biomicroscopy findings, and device deficiencies.

Descriptive summaries (counts and percentages) for ocular and nonocular AEs will be presented by Medical Dictionary for Regulatory Activities (MedDRA) Preferred Terms. In addition to an overall presentation of AEs, reports will be generated for serious AEs. AEs leading to study discontinuation will be identified. Individual subject listings will be provided, as necessary.

Individual subject listings will be provided for AEs that occur after signing informed consent but prior to exposure to study lens care solutions.

Each biomicroscopy parameter will be tabulated by its grade. For each biomicroscopy parameter, counts and percentages of eyes that experience an increase of ≥ 2 grades from baseline to any subsequent visit will be presented. Baseline is defined as Visit 1. A supportive listing will be generated which will include all biomicroscopy data from the affected visit for those eyes experiencing the increase of ≥ 2 grades, with the following variables: lens care solution, Investigator, subject, age, sex, visit, eye, parameter, baseline value, and value at the visit.

Two listings (prior to exposure of investigational products, and treatment-emergent) of device deficiencies, as recorded on the device deficiency Form, will be provided. Additionally, each device deficiencies category will be tabulated.

No inferential testing will be done for safety analysis.

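### SAP 5.3.2 limits the biomicroscopy grade and shift tables to Baseline and Day 30, so a 1-grade worsening seen only at an unscheduled visit (or at an early exit not counted as Day 30) reaches no biomicroscopy table

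*SAP*

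**What the plan says.** SAP 5.3.2 defines four biomicroscopy outputs, with Visit 1 as baseline.

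- Grade table: "Each biomicroscopy parameter will be tabulated by its grade, at Baseline and Day 30".
- Shift table: "A shift table showing grade at baseline relative to Day 30 will also be presented for each parameter".
- Marked-increase table: "counts and percentages of eyes that experience an increase of ≥ 2 grades from baseline to any subsequent visit will be presented".
- Listing for the eyes in the marked-increase table: "A supportive listing will be generated which will include all biomicroscopy data from the affected visit".

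Protocol 11.7 has the same marked-increase table and listing. Its grade table carries no visit limit: "Each biomicroscopy parameter will be tabulated by its grade". It has no shift table.

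Slit-lamp examinations also take place away from Day 30. The procedures for all unscheduled visits in Protocol 10.3 include "Perform biomicroscopy". For early exits, Protocol 10.4 says "Any subject who exits early from the study should undergo all procedures outlined at Visit 3/Exit", and the Visit 3 procedures in Protocol 10.2.3 include biomicroscopy. Protocol 10.3 gives a subject who leaves at an unscheduled visit a separate Early Exit form. Neither document says whether that examination counts as Day 30 in the tables.

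The eligibility limit, in Protocol 8.2, excludes "Biomicroscopy findings observed during the Visit 1 slit-lamp examination that are moderate (grade 3) or worse in either eye".

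**The concern.** Visits outside the schedule are often made because something is wrong with the eye. Two of the three biomicroscopy tables do not name those visits. The third counts only rises of 2 or more grades. Lesser worsening found at such a visit can therefore go unreported in every biomicroscopy table, even where it takes the eye to a grade that would have kept it out of the trial.

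Safety in this trial is purely descriptive: Protocol 11.7 plans no inferential testing and SAP 5.2 states no safety hypothesis. The tables are therefore the main safety evidence from the slit lamp. A Day 30 table describes eyes still under observation at Day 30, which is a narrower group than the eyes exposed to the product. The primary CLDEQ-8 analysis is not affected.

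**Working it through.** The plan gives no figure to reproduce on this point. The check sets each output against each type of visit, then asks which changes in grade are left uncovered.

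**Step 1. Outputs against visits (SAP 5.3.2; Protocol 10.3, 10.4)**

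| Output | Day 30 visit | Unscheduled visit | Early exit |
|---|---|---|---|
| Grade table | yes | no | not stated |
| Shift table | yes | no | not stated |
| Increase of 2 or more grades | yes | yes | yes |
| Listing | only eyes with that increase | only eyes with that increase | only eyes with that increase |

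**Step 2. Changes in grade**

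The documents do not give the grading scale. Assume whole grades from 0 to 4. Eligible eyes start at 0, 1 or 2, which leaves nine possible worsenings.

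- Rise of 2 or more grades: 0→2, 0→3, 0→4, 1→3, 1→4, 2→4. These six are counted and listed at any visit.
- Rise of 1 grade: 0→1, 1→2, 2→3. These three appear in no biomicroscopy table if seen only at an unscheduled visit, or only at an early exit that is not treated as Day 30.

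The 2→3 case matters most. It reaches the Visit 1 exclusion level, yet an eye that starts at 2 enters the any-visit count only at grade 4.

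**Step 3. How many eyes could lack a Day 30 row**

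Inputs are about 120 randomized and about 110 completed (Protocol 8, SAP 1.2).

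- Non-completers: 120 − 110 = 10 subjects, or 10 × 2 = 20 eyes.
- If all 10 left while using the same product, all 120 subjects had been exposed to it: 20 / 240 = 8.3% of its eyes.
- If 5 left on each product, 10 eyes per product are affected. Between 0 and 5 subjects would have left in Period 1 on the other product, so 115 to 120 subjects (230 to 240 eyes) were exposed: 10 / 240 = 4.2% to 10 / 230 = 4.3%.
- If early-exit examinations are treated as Day 30, the figure falls towards 0.

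These are eyes that might lack a Day 30 row, whatever the reason for leaving. They are not eyes with a finding. Someone who leaves in Period 1 is never exposed to the second product and rightly has no row for it. Someone who leaves in Period 2 keeps the Period 1 row.

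Completers can be affected too. A 1-grade rise seen at an unscheduled visit and gone by Day 30 leaves the denominator unchanged but is not shown. The documents give no basis for estimating how often this happens.

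**The case against.** The case for leaving the SAP alone is substantial, and most of it stands.

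- A reader might infer from the Day 30 wording that off-schedule findings vanish from the tables altogether. They do not. The any-visit count and its listing catch every rise of 2 or more grades.
- Protocol 12.2 requires a clinically relevant untoward change in a study parameter to be reported as an adverse event. Protocol 10.4 requires signs suggesting intolerance to be recorded on an AE form. SAP 5.3.1 summarizes ocular events by eye and identifies those that led to discontinuation. A wearer who stops because of an eye reaction should appear there.
- A reader might also infer that people who leave early are dropped from the safety population. SAP 2.1 defines that set by exposure, so they remain in it. At most they are absent from two tables.
- The SAP's silence on early exits is not an exclusion. Because those subjects follow the Visit 3/Exit procedures, a programmer might reasonably place the examination at Day 30.
- The SAP keeps the Protocol's any-visit rule intact and adds a shift table that the Protocol did not ask for.

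The remaining gap is narrow. The AE route depends on the Investigator's judgment and reports preferred terms, so it cannot stand in for a table of grades. The Protocol synopsis promises supporting listings for each safety variable, but SAP 5.3.2 specifies a biomicroscopy listing only for the markedly worsened eyes. Placing early exits at Day 30 would still leave out unscheduled visits.

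**Conclusion.** The point holds in a limited form. The grade and shift tables are confined to Baseline and Day 30, where Protocol 11.7 sets no visit limit for the grade table. As a result, a 1-grade worsening seen only off schedule, including 2→3, has no place in any biomicroscopy table.

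The ceiling on eyes missing from a product's Day 30 denominator through non-completion is about 20 of 240 (8.3%), reached only if every non-completer left on that product and no early-exit examination is counted as Day 30. The number of eyes with an actual unreported finding is unknown.

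It is tempting to conclude that the loss flatters CCP, on the view that a new peroxide product prompts more exits than a familiar solution. The documents do not support this. Protocol 5.2 describes reactions to peroxide misuse, but it also calls the overall risks of the two products similar when used as indicated. No exit rates by product are given.

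The conclusion assumes a whole-grade scale. Grade 3 is an eligibility limit at Visit 1; the documents do not call it a safety threshold during follow-up. This is an inexpensive improvement to descriptive reporting and does not bear on whether the trial succeeds.

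**What to change.** In SAP 5.3.2, keep the Day 30 tables and add, for each parameter and each product in use, a grade and shift table based on the worst post-baseline grade.

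- Visits: all visits in that product's period, including unscheduled and early-exit visits. The Visit 2 examination belongs to Period 1.
- Denominator: all eyes exposed to that product that have at least one post-baseline examination in its period. Show the number of exposed eyes without one.
- The count of eyes at grade 3 or worse can be read directly from this table, so no separate output is needed.

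The same edit can state in one sentence whether an early-exit examination counts as Day 30 in the existing tables.

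The cost is SAP wording and one extra descriptive output per parameter, from examinations the protocol already requires. Eyes examined more often have more chances to show a high worst grade, so the new table should be read beside the Day 30 tables and not in place of them.
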